4.1. Study 1. Evaluating the Diagnostic Accuracy of CoCoA-PAD subtests

Participants

A total of 120 participants will be recruited: 60 participants with subjective cognitive decline (SCD) and 60 participants with mild cognitive impairment (MCI). Participants will be classified post-recruitment into four distinct diagnostic groups: healthy controls, preclinical AD, prodromal AD, and non-AD related MCI. Figure 3 provides a flow of the estimated frequencies of each diagnostic group within the sample.

Sampling

This study will use a stratified sampling approach with post-hoc diagnostic classification. A prospective quasi-experimental between-group research design will be employed.

A stratified sampling approach will ensure that key demographic information, including years of education and ethnicity, will match national population demographics of the UK. 2021 census data revealed that 6% of 70–74-year-olds in the UK are from non-white ethnic minority backgrounds. However, given that people from minority ethnic backgrounds are significantly more likely to have dementia but less likely to receive a diagnosis (Okeoghene Ighomereho, 2025), for the purpose of this study, the stratified sampling target will be inflated to 10%.

Similarly, 2021 census data has mapped the educational attainment of the UK population. No age-specific education attainment values were published, but regional values have been published, and Plymouth demographics have been selected for this study. This is based on coastal communities having higher rates of dementia, lower rates of diagnosis, and significant social inequalities which often exclude them from research (Alzheimer’s Research UK, 2024). This study will replicate educational attainment values, with provision for 5% variation in the recruitment to each education level – see Table 1.

Table 1. Educational Attainment and Stratified Sampling Target

Educational Attainment	Plymouth Demographics	CoCoA-PAD Recruitment Target Range
No Qualification	17%	14-26
Level 1 (O level any grade)	10%	6-18
Level 2 (O levels passes)	14%	11-23
Apprenticeship	6%	1-13
Level 3 (A level equivalent)	17%	14-26
Level 4 (3 rd level qualifications)	34%	35-47
Other	2%	0-8

Procedure

Participants will be recruited and classified post-recruitment into diagnostic groups on the basis of AD biomarker results (pTau-217) and performance on the M-ACE, using a cut-off score of 20 for MCI (Potts et al., 2022).

Measures

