4.6. Bias Reducing Factors

Several different methods have been used to ensure as many confounding variables as possible are controlled for.

Sampling Procedure

- A stratified research design will be used to ensure the research sample is representative of UK demographics for ethnicity and low educational attainment, both of which are risk factors for Alzheimer's disease and frequently under-represented in research (Chan et al., 2024).
- The All-Party Parliamentary Group on Dementia (2023) report outlined that access to transport is a key barrier that prevents or delays people living in rural and coastal communities for receiving a diagnosis of dementia. To ensure people with poor transport access are not excluded from this study, this study includes the option for all participants to travel to the research sites via taxi, at no cost to the participant.
- All data collected in Study 1 and Study 2 will be collected blind to the participants AD biomarker status. The AD diagnosis will be determined after the entire Study 1 and 2 samples are collected, when the AD biomarkers will be sent to the Dementia Biomarker Factory for analysis.
- Participant diagnostic status will be determined using objective criteria based on AD biomarker status and established cut off scores for MCI on the Mini Addenbrooke's Cognitive Examination (M-ACE) note that English as a first language is an inclusion criterion for this study. This is due to the confounding impact of performing cognitive assessments in a non-native language. Subsequent research will aim to adapt the CoCoA-PAD assessment so that it can be administered and scored automatically in different languages, to minimise this source of bias in the future.

Accessibility

All participant facing documents have been coproduced by members of the PPI group, who have 'signed off' on the research poster, participant information sheet, and debrief document.

Standardisation

- The recruitment screening and assessment battery will be heavily standardised and will use an assessment script (CRF). This will ensure consistency in screening and data collection for all participants.
- The scoring of all CoCoA-PAD tests will be completed using validated automated procedures, which reduces the potential for human error.

Data Analysis

- The full analysis plan will be reviewed by a statistician and approved.
- The full analysis plan will be pre-registered on the Open Science Framework.

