With regards to how cognitive impairment is classified, the authors state that 'cognitive tests for individuals with MCI are typically 1 to 1.5 standard deviations below the mean for their age and education matched peers on culturally appropriate normative data'.

Table 3 provides a breakdown of the specific inclusion and exclusion criteria used in the CoCoA-PAD study.

Table 3. Recruitment Criteria for Subjective Cognitive Decline and Mild Cognitive Impairment

Subjective Cognitive Decline	
Inclusion Criteria	Exclusion Criteria

 • >3.38 on IQCODE Self-Report items 1-7 (PROTECT) OR 
 • ≥ 4 on SCD-Q9 (non-Protect) AND 
 • Age ≥ 65 years • Onset of SCD within the last 5 years • English as a first language • Normal demographically adjusted performance on standardised cognitive tests • Specific Race and Education (using stratified sampling approach) 	
 • Cognitive impairment, i.e., performance ≥ 1 SD below demographically adjusted norms (PROTECT) OR 
 • ≤ 17 on the telephone MoCA (non-PROTECT) AND 
 • Lacks mental capacity to consent to research • Diagnosis of dementia • Sensory impairment that cannot be corrected for with sensory aids, e.g., blindness. • Previous neurological injury (stroke, traumatic brain injury, severe epilepsy, brain tumour)

	
 • Other neurodegenerative syndrome (e.g., Parkinson's disease, multiple sclerosis, etc) • Diagnosis of learning disability • Severe depression (PHQ-9\geq15 OR score \geq1 on PHQ-9 suicide question) • Current severe psychiatric disorder (bipolar disorder, schizophrenia, or psychotic disorders) • Current drug or alcohol abuse • Untreated diagnosis of sleep apnoea.
Mild Cognitive Impairment	
Inclusion Criteria	Exclusion Criteria

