6.5. Informed Consent

All research appointments at the Plymouth site will take place at the Brain Research and Imaging Centre (BRIC). Data collection at the Devon and North East London sites will be conducted by local NHS research teams in NHS clinical settings. The environment will be quiet and distraction free. At the beginning of the session the investigator will read through the relevant information sheet with the participant and answer any questions. For participants with a mild cognitive impairment, a mental capacity assessment will be completed again. For participants who demonstrate mental capacity to participate, and who indicate their willingness to do so, they will be asked to review the electronic consent form (see Electronic Consent Form).

Informed consent will be documented using the REDCap secure electronic data capture system, hosted on University of Plymouth servers. The consent form will display version and date control, and the wording is identical to the Electronic Consent Form attachment. Participants will be required to tick each statement. An electronic signature will be collected using a finger or stylus signature and stored securely in the REDCap database. An audit trail will record the date and time and identity of the consenting individual. The process allows participants to ask questions before completing consent, ensuring compliance with the Joint statement on seeking consent by electronic methods ([hra-mhra-econsent-statement-sept-18.pdf](https://www.hra-nhs.uk/consult/ia/pdfs/hra-mhra-econsent-statement-sept-18.pdf))

At the point of consent, participants will be asked whether they wish their General Practitioner (GP) to be informed of their participation in this research. This is optional and will not affect eligibility or clinical care. Where a participant provides explicit consent, a brief notification letter will be emailed to their GP at the time of consent, confirming study participation and outlining that the research is observational, does not alter routine care, and that no clinical results will be returned. No notification will be sent without the participant's explicit consent.

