Although blood tests are common medical procedures, they can cause psychological distress for some participants. Common reactions include anxiety, nervousness, or anticipatory stress, particularly among individuals with needle phobia (trypanophobia) or a history of negative medical experiences. Some participants may feel faint, dizzy, or panicked before or during the procedure.

To minimise psychological distress, all blood tests will be conducted by trained clinical research staff, such as NHS phlebotomists or nurses, who are experienced in working with older adults. Participants will receive clear, simple explanations of the procedure in advance, including reassurance that the test is safe and quick, and optional. They will have the opportunity to ask questions. During the blood draw, participants will be encouraged to sit or lie in a comfortable position, and will be monitored for signs of distress, dizziness, or fainting. If needed, breaks and recovery time will be provided. Researchers will take a calm and supportive approach throughout and ensure that the environment is as relaxed and non-threatening as possible.

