11.3. Sample Size

Given that there are three independent studies, a justification of the proposed sample is outlined for each study.

Study 1: Diagnostic Accuracy of CoCoA-PAD Subtests

The aim of this study is to test whether CoCoA-PAD subtests can distinguish between healthy controls (i.e., people with subjective memory problems without any evidence of AD biomarkers or cognitive decline) and people with preclinical and prodromal Alzheimer's disease. This study uses a prospective research design, and therefore exact participant numbers in each diagnostic criteria cannot be determined until after data collection. Figure 3 provides an estimate of the final sample composition, which includes of 36 healthy controls, 18 people with preclinical AD, and 40 people with prodromal AD. A power calculation using a fixed one-way ANOVA (estimated effect size $f = 0.33$ (moderate effect), $k = 3$) required a minimum sample of 90 to achieve the required power ($\alpha = 0.05$, $1-\beta = 0.8$). Based on current projections (36 controls, 18 preclinical AD, and 40 with prodromal AD), this would be achieved.

Study 2: The relationship between CoCoA-PAD subtests and the health of key brain regions

This study aimed to measure the strength of the association between key brain regions and performance on CoCoA-PAD subtests. It includes a subgroup of study 1 participants. A power calculation using a linear multiple regression (fixed model, single regression coefficient, effect size f^2 (0.1, small) required a minimum sample of 64 participants to achieve the required power ($\alpha = 0.05$, $1-\beta = 0.8$).

Study 3: Testing whether CoCoA-PAD is sensitive to pathological cognitive decline in AD

This study aimed to compare 1 year change score (time 2 score – time 1 score) on CoCoA-PAD subtest scores in people with early Alzheimer’s disease and healthy controls. It includes a subgroup of study 1 participants. A power calculation using a matched pairs *t* test (Cohen’s *d* = 0.5 (moderate)) required a sample of 27 to achieve the required power ($\alpha = 0.05$, $1-\beta = 0.8$).

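### The blood test is presented to participants as optional and is not mentioned in the entry criteria, yet Study 1 classification and Study 3 selection both need pTau-217

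*Protocol*

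**What the plan says.** Section 7.5 (Participant Distress, Blood Test) describes what participants hear before the draw, "including reassurance that the test is safe and quick, and optional".

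Section 4.1 classifies participants after recruitment "on the basis of AD biomarker results (pTau-217) and performance on the M-ACE". Section 4.6 repeats the rule: "Participant diagnostic status will be determined using objective criteria based on AD biomarker status". Neither gives a route to a group without a biomarker result. Section 4.3 takes the 18 healthy controls and 18 people with prodromal AD for Study 3 from that classification.

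Table 3 (section 5.5) has no line on giving blood for either the SCD or the MCI group. Its only consent-related item is an exclusion: "Lacks mental capacity to consent to research".

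Other sections treat the sample as routine. Section 6.6 lists the blood test for all sites and drops only the MRI outside Plymouth. Section 10.3 says consent is obtained for plasma collection, analysis and storage. Section 6.5 says of the consent form: "Participants will be required to tick each statement".

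The target in section 4.1 is 120 recruited (60 SCD, 60 MCI), split in section 5.1 into 81, 19 and 20 by site. For Study 1, section 11.3 projects 36 healthy controls, 18 preclinical AD and 40 prodromal AD, and states that the calculation "required a minimum sample of 90 to achieve the required power".

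**The concern.** A sample that participants are told they may skip is the one measurement without which they have no diagnostic group. Someone who meets Table 3 and declines blood could complete the cognitive battery and still be missing from the preclinical and prodromal comparisons (primary objectives i and ii) and from selection for the one-year change study (objective iv). Secondary objectives ii and iii also need the pTau-217 result.

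The protocol has no rule for such a participant: no screening question, no replacement rule, and no target expressed as participants with plasma. The projected sample is close to the stated minimum and the preclinical group is only 18, so there is little room for avoidable loss.

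**Working it through.** **Inputs.** From section 11.3: projected groups 36 + 18 + 40 = 94; f = 0.33; k = 3; alpha 0.05; target power 0.80; stated minimum 90. The share without plasma, q, is not in the protocol. It is an assumption here, shown over 2% to 20% and spread evenly over the groups.

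**Reproducing the plan's figure.** For a fixed one-way ANOVA, power comes from the noncentral F distribution with 2 and N − 3 degrees of freedom and noncentrality N × f².

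- N = 90: 90 × 0.33² = 9.80; power 0.793.
- N = 92: 92 × 0.33² = 10.02; power 0.802, the smallest N reaching 0.80.
- N = 94: 94 × 0.33² = 10.24; power 0.811.

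With f = 0.333 the smallest N is 90. The stated 90 therefore reproduces to within rounding of the effect size.

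**Margin.** 94 − 90 = 4, and 4/94 = 4.3%. Against the recomputed 92, 94 − 92 = 2, and 2/94 = 2.1%.

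**Effect of missing plasma.** Expected N = 94 × (1 − q), rounded down for the power calculation. Preclinical group = 18 × (1 − q).

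| q (assumed) | 94 × (1 − q) | N used | Power | Preclinical |
|---|---|---|---|---|
| 0% | 94.0 | 94 | 0.811 | 18.0 |
| 2% | 92.1 | 92 | 0.802 | 17.6 |
| 5% | 89.3 | 89 | 0.788 | 17.1 |
| 10% | 84.6 | 84 | 0.761 | 16.2 |
| 20% | 75.2 | 75 | 0.708 | 14.4 |

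**Possible hidden allowance.** If the controls and the preclinical group both come from the 60 SCD recruits, the text places 36 + 18 = 54 and leaves 6 (10%) unplaced. Section 11.3 does not say what they are. They may allow for missing or grey-zone results; if so, the table overstates the loss.

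**Setting the passages side by side.** If a mandatory consent statement covers blood, the test is in effect an entry condition and section 7.5 describes it wrongly. If none does, nothing in the eligibility or consent text secures the sample. The sections need reconciling in either case.

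**The case against.** The best defence is that blood is already a normal part of taking part. It is in the appointment schedule at every site, in the information sheet read before screening (section 7.2), and in the plasma consent of section 10.3. On that view, the word optional in a passage about reducing distress means only that a frightened person may refuse on the day, which any voluntary study must allow. That is a plausible reading, but it is not what section 7.5 says. The tick-every-statement rule does not settle it either: the form is not available, and other agreements sought at consent are a matter of choice (GP letter, section 6.5; PROTECT data sharing, section 9.5).

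Several stronger readings are tempting and should be resisted.

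- A reader might infer that decliners count towards the 120. No sentence says so. The inference comes from a target set on recruitment and the absence of a replacement rule.
- A reader might infer that tired, anxious or more impaired participants will refuse selectively because blood follows the long battery. The protocol offers no evidence of this. Section 6.6 provides regular breaks, fatigue checks and the option of two sessions.
- A reader might infer that Study 1 will be underpowered. That needs a refusal rate the protocol does not give, and even a 5% loss costs only about half a percentage point of power relative to the stated minimum of 90 (0.788 against 0.793).

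It can also be said that section 11.1 leaves missing data to the pre-registered analysis plan. That covers how missing results are analysed. Eligibility, consent wording and recruitment targets belong in the protocol.

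**Conclusion.** The point holds as an inconsistency with a practical consequence: the protocol calls the sample optional in one place, omits it from eligibility, treats it as standard elsewhere, and cannot classify anyone without it. A decliner is lost to primary objectives i, ii and iv, though not to the usability objective or, at Plymouth, to the Study 2 associations.

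The size is modest and conditional. It assumes that the 94 contains no allowance for missing plasma and that losses fall evenly across groups. The protocol supports neither a forecast of how many will decline nor a claim that they will differ from the rest. The reason to act is that the spare margin is four people, the smallest group is 18, and prevention is nearly free.

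**What to change.** 1. Add to Table 3, for both the SCD and MCI groups: willing at screening to provide a blood sample for pTau-217.
2. Reconcile section 7.5 with sections 6.5, 6.6 and 10.3. State that a participant may decline on the day without penalty, but that the sample is needed for Study 1 classification. Check that the consent form says the same.
3. While recruitment is open, track participants with a plasma sample, not only participants recruited, against the 120 and the site targets of 81, 19 and 20. Whether a sample was taken is known at the appointment. Table 5 sends plasma for analysis in May 2027, the month Study 1 and 2 data collection ends, so a shortfall first noticed then would be hard to repair.

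The cost is one eligibility line, a wording change by amendment and one extra recruitment count. A few volunteers unwilling to give blood would not be enrolled, including some who could have contributed to usability or Study 2.

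Refilling places is a separate choice with its own cost and is not essential to this fix. Keeping 90 in the three groups would take 120 × (90/94)/(1 − q) recruits: 121 at an assumed 5% loss, 128 at 10%.

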7.6. Recording Adverse Effects

“An adverse event (AE) is any untoward medical occurrence in a patient or clinical investigation subject administered a pharmaceutical product which does not necessarily have a causal relationship with this treatment.” (ICH-GCP E6(R2), Section 1.2).

This study will include close monitoring of adverse effects. A brief adverse event checklist will be administered following each of the research procedures (neuropsychological assessment, MRI scan and blood test), see CoCoA-PAD Adverse Event Checklist.

Adverse effects will be classified as mild, moderate, severe and serious. The classification framework for AEs is outlined in Table 4. Mild AEs, such as transient discomfort or low-level anxiety, will be recorded in the adverse event log and monitored locally, with appropriate reassurance or breaks offered to the participant. Moderate AEs, which may cause temporary interference with study participation or require minimal intervention (e.g. dizziness, distress), will be recorded in the adverse event log and followed up to resolution. Severe or serious adverse events (SAEs) including those requiring medical attention or resulting in withdrawal from the study, will be reported to the sponsor within 24 hours and reviewed for potential onward reporting to the Research Ethics Committee (REC) within 15 days, in line with governance requirements. All AEs will be reviewed during the monthly Trial Management Group and the bi-yearly Project Steering Group meetings. Where feasible, the research protocol will be amended to reduce the likelihood of moderate or severe future adverse events, and participant safety will remain the primary consideration in all procedural decisions.

Table 4. Classification of Adverse Events

Severity Level	Definition	Example Events
Mild	An event that is easily tolerated, causes minimal discomfort, and does not interfere with daily activities. No treatment or intervention is required.	Temporary low-level anxiety, minor bruising from blood draw, brief fatigue or headache
Moderate	An event that causes some interference with daily functioning or study activities and may require minimal intervention or advice.	Dizziness after blood draw, discomfort in MRI, need to stop a cognitive task due to distress
Severe	An event that causes marked limitation of activity, requires medical attention, or prevents continued participation. May result in study withdrawal.	Panic attack in MRI scanner, syncope, allergic reaction, serious psychological distress
Serious Adverse Event (SAE)	Any AE that results in death, is life-threatening, requires hospitalisation or prolongs existing hospital stay, causes disability/incapacity, or is a congenital anomaly.	Hospitalisation due to fall, life-threatening reaction, suicidal ideation requiring intervention

7.7. Disclosure of Research Data

Best practice guidelines on the disclosure of research findings to participants emphasise the importance of balancing ethical obligations to inform participants of their results, with the potential psychological, legal, and clinical consequences of disclosing uncertain or non-clinically validated information. The Wellcome Trust and Medical Research Council (MRC) Framework on the Feedback of Health-Related Findings in Research (2014) outlines clear ethical conditions under which individual research results should be disclosed to participants. Feedback should only be provided when three key criteria are met: analytical validity, clinical significance, and actionability. This means that any findings must be generated using reliable, validated methods; must have clear and serious implications for the participant's health; and must point to a condition for which effective treatments or preventive actions are available. The framework strongly advises against disclosing results that are uncertain, not clinically validated, or non-actionable—particularly when they are generated in a research-only context (such as in a non-

clinically accredited laboratory). It also emphasises that participants should be informed during the consent process about what types of results may or may not be disclosed. Feedback, when given, should be delivered by appropriately trained professionals and should include a clear pathway for follow-up care if needed. This approach ensures that participants are protected from unnecessary anxiety or harm while upholding ethical transparency.

The appropriateness of disclosure of data from the CoCoA-PAD study has been considered carefully.

MRI Data Disclosure

Some participants in the study will undergo structural MRI scans; however, no individual feedback will be provided from these scans. This is because the MRI data will not be reviewed or interpreted by a qualified medical professional such as a neurologist or neuroradiologist, and therefore any feedback would be speculative and ethically inappropriate. Nevertheless, there is a safety protocol in place: if the radiographer operating the scanner, who is an NHS professional radiographer registered with the Health and Care Professionals Council and employed by University Hospitals Plymouth NHS Trust observes any incidental findings of potential clinical concern during acquisition (e.g., possible tumours or significant abnormalities), they will follow the local NHS policy for flagging these findings to the participant's GP. Participants have the option to opt-in to finding out if their GP has been notified. If they opt in, the participant will be informed whether any information has been shared with their GP at the feedback meeting. This disclosure will be scripted and will follow the process outlined in the MRI Disclosure document. Given that this information will not be medically verified by a professional trained in interpreting MRI scans, participants will not be provided with any clinical details regarding the unexpected finding on their scan. This process is outlined on the participant information sheet.

Biomarker Data Disclosure

The disclosure of biomarker results, such as plasma pTau-217 levels, must be approached with care, particularly in light of evolving ethical guidance. Current best practice (see Largent et al., 2023) supports offering disclosure protocols to individuals with cognitive difficulties, where appropriate, as disclosure can help people better understand their condition, make informed decisions about future care, and implement lifestyle changes that may support cognitive health. This position is also supported by the Patient and Public Involvement (PPI) group involved in this study, who advocate for responsible and transparent communication of biomarker findings in individuals experiencing cognitive symptoms. Biomarker disclosure is not recommended for cognitively healthy individuals. For this group, the risks include increased anxiety, potential psychological distress, insurance and employment discrimination, and the lack of clinical certainty regarding prognosis, particularly given the low conversion rate from biomarker positivity to dementia in cognitively intact populations.

In the CoCoA-PAD study, we have weighed the potential advantages against the risks to develop a biomarker disclosure procedure. Although pTau-217 using the ALZpath Simoa immunoassay, processed on Quanterix's Simoa HD-X platform, has demonstrated research validity, it is not

currently licenced or approved for clinical use in the UK, and the UKRI Biomarker Factory at UCL is not a licenced laboratory for clinical work. Following consultation with the UKRI Biomarker Factory team, they explicitly stated that the biomarker results must not be disclosed under any circumstances, as a condition of their use.

Based on the Wellcome Trust and MRC criteria for disclosure (2014), the pTau-217 biomarker used in this study does not meet the criterion for '*analytical validity*' or '*clinical significance*'. As such, the CoCoA-PAD team have concluded that the risk of iatrogenic harm caused by disclosing biomarker results outweighs the potential benefits, and therefore, biomarker results will not be disclosed to CoCoA-PAD participants.

It is important to note that the validity of pTau-217 is a rapidly developing topic. The biomarker analysis for this study is not expected to take place until May 2027. If, during this time, the pTau217 assay being used is approved for clinical use, and the UKRI Biomarker Factory becomes a clinically approved laboratory, a substantial amendment to the CoCoA-PAD protocol will be submitted to the research ethics committee, outlining a revised biomarker disclosure procedure with significant PPI input.

Cognitive Staging Disclosure

As part of the study protocol, all participants will undergo cognitive screening using the Addenbrooke's Cognitive Examination – Third Edition (ACE-III). This is a widely validated cognitive screening tool that provides a detailed assessment of five cognitive domains: attention, memory, verbal fluency, language, and visuospatial function. The ACE-III is extensively used across UK memory services, particularly within specialist settings where a more detailed cognitive profile is clinically useful. It is the primary cognitive screening instrument used within NHS memory clinics in the local region, including Devon Partnership NHS Trust, Cornwall Partnership NHS Foundation Trust, Livewell Southwest, and University Hospitals Plymouth NHS Trust.

Participants will be provided with the option of receiving feedback on their M-ACE assessment results. This will be reviewed with on the PIS on both the day of data collection. Participants who consent to receive feedback, will receive individualised feedback on the results of their ACE-III assessment. This feedback will include a clear and supportive explanation of whether their results suggest:

- A cognitive profile within expected limits for age and education
- A profile consistent with Mild Cognitive Impairment (MCI)

Although MCI is a label that it often used in practice, it is a descriptive label to refer to people with cognitive difficulties, and it does not specify a cause or underlying pathology. It is important to note that participants will not be given a diagnostic label or interpretation regarding the cause of any difficulties. Participants who receive feedback indicating possible MCI will be provided with a lay summary information sheet, explaining what MCI is, how it differs from normal ageing and dementia, and evidence-based brain health and lifestyle

strategies to support cognitive wellbeing. All feedback will be delivered in a sensitive, person-centred manner, and with a written feedback summary. Participants will be provided with information about the referral route for a memory assessment, should they wish to undergo a clinically assessment with a memory service.

This feedback will be primarily provided by the Chief Investigator, a qualified clinical neuropsychologist with substantial experience in cognitive assessment and communicating results to patients and their families. For sites outside of the primary research centre, feedback will either be delivered directly by the Chief Investigator or by a local research nurses trained and supervised by the Chief Investigator.

This approach reflects ethical guidance that supports sharing clinically meaningful information with participants when it is generated using validated tools, has clear interpretive value, and can support health literacy and informed decision-making.

CoCoA-PAD Disclosure

The study also includes novel digital cognitive assessments developed under the CoCoA-PAD protocol. These assessments are research tools under development and currently lack an any normative data or diagnostic benchmarks to interpret results in individual participants. Without reference values or validated clinical thresholds, it is not possible to determine what constitutes 'normal' or 'impaired' performance in the older adult population. Therefore, results from these digital cognitive tasks will not be disclosed to participants, as doing so would be speculative.

